### 2.2. Secondary Objectives

- 1) Assess the difference in adherence to regorafenib between the two groups. Pill counts will be used to assess adherence. The hypothesis is that Ginseng may increase adherence by decreasing fatigue.
- 2) Assess the difference in toxicities between the two arms.
- 3) Assess the difference in retention between the two arms. Retention is the proportion of subjects who complete the study. Note that they may not completely adhere to the study medication, but as long as they come in for the last measurements, they are considered retained.
- 4) Assess response rate and overall survival

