## **11 STATISTICAL CONSIDERATIONS**

### **Power/Sample Size:**

The pilot study will enroll 90 total subjects and randomize them using a 2:1 allocation with 60 subjects enrolled in the Regorafenib + Ginseng group and 30 enrolled in the regorafenib + no ginseng group. The sample size is calculated based on the MFSI-SF fatigue endpoint. Based on the data published in Barton et al (2013), the expected standard deviations for the outcome of interest are 27.0 for the Ginseng group and 26.1 for the no ginseng group. Using a two group Satterthwaite t-test with a 0.050 two-sided significance level, there is 80% power to detect a difference between groups if the change in the no ginseng group is 10 and the change in the Ginseng group is 27 (or greater) (a group difference of 17 units). In addition, with this sample size, a two-sided 95.0% confidence interval for the difference of the two means (change in fatigue score for Ginseng group vs. change in fatigue score for no ginseng group) will extend 11.833 from the observed difference in means, assuming that the common standard deviation is 27.0 (conservatively choosing the standard deviation from the Ginseng group since it is larger than the no ginseng standard deviation) when the sample sizes are 60 and 30 respectively (a total sample size of 90) and the confidence interval is based on the large sample z statistic.

Based on previous published data [1] we believe that the Ginseng mean change in fatigue score will likely be closer to 20 (rather than 27); thus, we do not anticipate that this trial will reach

statistical significance. However, we will be able to refine our estimate of the standard deviation for the fatigue score in this subject population and provide a 95% confidence interval to estimate the likely boundaries for the true effect size. This information, along with estimates of retention and adherence, can be used to determine the sample size for further evaluation.

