### **The secondary objectives are as follows:**

(1) To assess the difference in adherence to regorafenib between the 2 groups. We will assess regorafenib adherence at three times, at the end of the 3rd week of each cycle. Since the recommended dose is once daily for 21 days, a measure of adherence would be the number of pills (out of 21) that each subject takes during each cycle. Using this measure for each subject, we will first compare groups using a 2-sample t-test for cycle 1, cycle 2 and then overall. Next, we will define subjects as being adherent based on having taken their pills on 17 (or more) days out of 21 (i.e. over 80% adherence). Using this definition of adherence, we will fit a 2x2 table comparing adherence rates between groups using a 1 degree of freedom Chi-square test. In addition, the statistician will compare mean daily doses using a t test and median daily doses by using Mann-Whitney test. Our hypothesis for these analyses is that Ginseng will reduce fatigue and thus lead to greater adherence to regorafenib in subjects who are in the Ginseng arm when compared to the no ginseng arm

(2) To assess the difference in toxicities between the two arms. Fisher exact tests will be used to assess the difference in toxicities between the two groups as well as the proportion of subjects

who experience grade 3 or higher toxicities of any kind according to the data safety monitoring plan described below.

(3) To assess the difference in retention between the two arms. As subjects can drop out of the study at various times, we will use Kaplan-Meier methods to estimate the retention distributions in each group and a log-rank test to assess the difference in distributions between the two groups.

(4) Response rate and overall survival are secondary objectives for the trial. Overall survival (OS) as an endpoint is defined in section 8.2.8 of the protocol. OS will be estimated using the Kaplan-Meier method and 90% confidence intervals derived as described in Brookmeyer and Crowley. The median will be provided along with the corresponding 95% CI. Additionally, the 25% and 75% percentiles for these endpoints will also be provided.

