Response rate (RR) as an endpoint is defined in section 8.2.5 of the protocol. Objective response (complete response + partial response) rate defined as the proportion of patients who achieve an objective response out of all patients treated on that arm will be estimated along with a 95% confidence interval.

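### The toxicity objective is planned as Fisher exact tests alone, with no estimate of the difference and no confidence interval, so a non-significant result would not rule out a large excess of Grade 3 or higher toxicity

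*Combined protocol and SAP*

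**What the plan says.** Section 2.2 lists as the second secondary objective: "Assess the difference in toxicities between the two arms". Section 11, Analyses, secondary objective (2), gives the method: "Fisher exact tests will be used to assess the difference in toxicities between the two groups as well as the proportion of subjects". The rest of that sentence defines the proportion by severity and points to a later section: "who experience grade 3 or higher toxicities of any kind according to the data safety monitoring plan described below". No effect measure, interval, test level, sidedness or expected rate is given for toxicity.

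The cross-reference leads to Sections 12.1 and 12.2. These describe oversight and the timing of reports, and contain no toxicity estimate or threshold. The institutional monitoring plan named in Section 12.1 is not part of the documents.

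The sample size was set on the MFSI-SF fatigue score only, with a "2:1 allocation with 60 subjects enrolled in the Regorafenib + Ginseng group and 30 enrolled in the regorafenib + no ginseng group". For fatigue, Section 11 says that significance is not expected and relies on a 95% confidence interval for the difference between arms. For response rate, each arm's rate "will be estimated along with a 95% confidence interval".

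**The concern.** The objective asks about a difference. A Fisher test says whether a difference was detected; it does not say how large a difference the data allow. In a trial of 90 subjects the likely result is a p-value above 0.05, and from that alone a reader cannot tell a well-bounded result from an uninformative one.

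The question has content here. Section 9.1 names possible ginseng effects, including interference with coagulation, hypoglycaemia and raised blood pressure, and Section 5.2.2 describes hypertension as a known adverse event of regorafenib. What is at stake is whether the report tells its reader how much added toxicity remains possible.

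**Working it through.** **Inputs from Section 11.** Arms of 60 and 30. For fatigue: "the expected standard deviations for the outcome of interest are 27.0 for the Ginseng group and 26.1 for the no ginseng group", "a group difference of 17 units", and "Using a two group Satterthwaite t-test with a 0.050 two-sided significance level, there is 80% power to detect a difference between groups".

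**Assumptions, because the documents are silent.**
- The Fisher test is two-sided at 0.05, carried over from the fatigue endpoint.
- The rise of interest is 20 percentage points. This is an illustration, not a threshold in the plan.
- The control rate of any Grade 3 or higher toxicity is varied from 5% to 75%. The only regorafenib Grade 3 rate in the documents is 9%, for fatigue alone (Section 1).

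**Step 1: reproduce the plan's own figures.**
- Standard error = √(27.0²/60 + 26.1²/30) = √(12.150 + 22.707) = 5.904, with Satterthwaite df ≈ 59.9.
- Noncentrality = 17/5.904 = 2.88, which gives 80.9% power. The plan says 80%.
- Half-width = 1.96 × 27 × √(1/60 + 1/30) = 11.833, as stated.

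Both agree. No corresponding figure is stated for toxicity.

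**Step 2: exact power of the Fisher test.** Power = Σ Bin(x; 60, p + 0.20) × Bin(y; 30, p), summed over all 61 × 31 tables with a two-sided Fisher p ≤ 0.05. The miss rate is 1 minus power.

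| Control rate p | Ginseng rate | Miss rate |
|---|---|---|
| 5% | 25% | 35% |
| 9% | 29% | 42% |
| 10% | 30% | 44% |
| 15% | 35% | 51% |
| 20% | 40% | 57% |
| 30% | 50% | 59% |
| 40% | 60% | 59% |
| 50% | 70% | 58% |
| 55% | 75% | 57% |
| 60% | 80% | 53% |
| 65% | 85% | 48% |
| 70% | 90% | 39% |
| 75% | 95% | 27.5% |

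Other settings:
- A one-sided 0.05 test misses 47% to 53% for control rates of 20% to 50%.
- Larger rises are found more often: power is 61% for 50% versus 75%, and 79% for 50% versus 80%.
- Smaller rises in less common events are found less often: 19% for 5% versus 15%, and 16% for 10% versus 20%.
- The rise detectable with 80% power is about 27 to 32 points for control rates of 10% to 60%.

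**Step 3: what an interval would show.** The Newcombe 95% interval for d = p₁ - p₂, with Wilson limits (l, u) for each arm, is
- lower = d - √[(p₁ - l₁)² + (u₂ - p₂)²]
- upper = d + √[(u₁ - p₁)² + (p₂ - l₂)²]

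Wilson limits: 42/60 gives 0.575 to 0.801; 30/60 gives 0.377 to 0.623; 15/30 gives 0.332 to 0.668.

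- Observed 42/60 (70%) versus 15/30 (50%): lower = 0.200 - 0.210 = -0.010; upper = 0.200 + 0.196 = 0.396. Fisher p = 0.10.
- Observed 30/60 versus 15/30 (50% in both): 0 ± 0.208, or -21 to +21 points.

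With equal observed rates, the upper limit is +12 points at 10%, +16 at 20%, +18 at 30%, +20 at 40%, and +21 at 50% and 60%.

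**The case against.** The strongest reply is that low power for a secondary toxicity comparison is ordinary in a 90-subject trial that calls itself a pilot and does not expect its own primary test to reach significance. That is true, and the point asks for no more subjects. But for fatigue the plan meets the same weakness with a confidence interval for the difference, and it does not do so for toxicity.

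Several further objections stand in part.
- **The size is conditional.** The miss rate rests on an assumed control rate, rise, level and sidedness, and about 59% is the highest value in the table. A reader might infer that the test misses such a rise about six times in ten whatever the setting; the calculation supports this only for control rates of about 20% to 55%.
- **Arm proportions may be reported.** The plan mentions the proportion with Grade 3 or higher toxicity. Given those proportions and the denominators, a reader could work out a difference and an interval. The plan does not require either.
- **Toxicity is not singled out.** The response-rate interval is for each arm, not for a difference. Adherence and retention are also compared by tests with no interval for the difference.
- **The protocol manages some of the risk.** Bleeding disorders and therapeutic anticoagulation are excluded, coagulation is monitored, and a monitoring committee receives reports at least twice a year. These are safeguards during the trial and do not estimate a difference at its end.

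A reader might also infer that this would be the only randomised safety comparison of the combination, because Section 11 says that an observed fatigue difference of 12 or more would make a follow-up trial unnecessary. That statement concerns evidence on fatigue. The difference that the plan expects is 8 to 12, for which it regards a follow-up trial as justified.

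**Conclusion.** The point holds as a gap in estimation. For an objective about a difference, the plan specifies a test and no estimate of the difference or its precision. Under the stated assumptions, a true 20-point rise would be missed 57% to 59% of the time at control rates of 20% to 55%, and less often outside that range. A non-significant p-value alone therefore does not rule out a large excess.

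Two stronger readings are not supported. The first is that the plan treats a non-significant test as evidence of safety; no sentence says so. The second is that a null result could say nothing about added harm. The same data, summarised by an interval, would bound the excess at roughly +12 to +21 points if the observed rates were equal and between 10% and 60%. This is a cheap improvement and does not invalidate the design.

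**What to change.** In Section 11, secondary objective (2):
- Make the main toxicity output the risk difference (ginseng minus no ginseng) for any Grade 3 or higher toxicity, with a two-sided 95% confidence interval by the Newcombe or Miettinen-Nurminen method.
- Give the same summary descriptively for the ginseng risks named in Section 9.1 under Precautions and Side Effects, with no claim of significance, so that no multiplicity rule is needed.
- Keep the Fisher p-value as supportive, and state its level and sidedness.
- Add a sentence such as: A non-significant test will not be taken as evidence of no added toxicity; the interval, including its upper limit, will be reported with any statement on safety.

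The cost is a few sentences and a few lines of code, with no new data or subjects. The change does not raise power: 80% power for 50% versus 70% would need about 77 control and 154 ginseng subjects (2:1, continuity-corrected), which is not proposed. It also sets no margin, so the result is an estimate and not a pass-or-fail finding. The small downside is that a wide interval will make the safety statement look less reassuring.

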## **12 TRIAL MANAGEMENT**

### **12.1 Data and Safety Monitoring Plan**

The study will be conducted in accord with the Comprehensive Cancer Center of Wake Forest University's Data and Safety Monitoring Plan.

HCRN oversight activities include:

- Review all adverse events requiring expedited reporting as defined in the protocol
- Notify participating sites of adverse events requiring expedited reporting
- Provide trial accrual progress and safety information to the sponsor-investigator
- Provide data summary reports to the sponsor-investigator
- Submit data summary reports to the lead institution Data Safety Monitoring Committee for review as per their DSMP.

### **12.2 DSMP Reporting Guidelines**

HCRN will compile data summary reports for this trial and submit these reports monthly to the sponsor-investigator. HCRN will submit data summary reports at a minimum twice a year to a Data and Safety Monitoring Committee (DSMC) associated with this protocol for review.

### **12.3 On-Site Monitoring**

Monitoring visits to the trial sites will be made periodically during the trial, to ensure all aspects of the protocol are followed. Source documents will be reviewed for verification of agreement with data as submitted via the data collection system. The site investigator/Institution guarantee access to source documents by HCRN or its designee and appropriate regulatory agencies. The trial site may also be subject to quality assurance audit by Bayer Pharmaceutical or its designee as well as inspection by appropriate regulatory agencies.

It is important for the site investigator and their relevant personnel to be available during the monitoring visits and possible audits and for sufficient time to be devoted to the process.

## **13 DATA HANDLING AND RECORD KEEPING**

### **13.1 Case Report Forms and Submission**

This study will utilize electronic case report form (eCRF) in the Hoosier Cancer Research Network (HCRN) electronic data capture (EDC) system. The EDC system is a comprehensive database used by HCRN. Access to the data through EDC system is restricted by user accounts and assigned roles. Once logged into the EDC system with a user ID and password, the EDC system defines roles for each user, which limits access to appropriate data. User information and passwords can be obtained by contacting HCRN at [contact].

Generally, clinical data will be electronically captured in the EDC system and correlative results will be captured in the EDC system or other secure database. If procedures on the study calendar are performed for standard of care, at minimum, that data will be captured in the source document. Select standard of care data will also be captured in the EDC system, according to study-specific objectives.

The completed dataset is housed at HCRN and is the sole property of the sponsor-investigator's institution. It should not be made available in any form to third parties, except for authorized representatives of appropriate Health/Regulatory Authorities, without written permission from the sponsor-investigator and HCRN.

### **13.2 Record Retention**

It is the expectation that all data has source documentation available at the site. The site must implement processes to ensure this happens.

Inspections by regulatory health authority representatives (i.e. FDA and IRB[s]) are possible. The site investigator should notify Bayer immediately of any such inspection.

To enable evaluations and/or audits from Health Authorities/HCRN, the site investigator agrees to keep records, including the identity of all participating subject (sufficient information to link records; e.g., hospital records), all original signed informed consent forms, copies of all source documents, and detailed records of drug disposition. To comply with international regulations, the records should be retained by the site investigator in compliance with regulations.

Essential documents shall be archived safely and securely in such a way that ensures that they are readily available upon authorities' request. Subject (hospital) files will be archived according to local regulations and in accordance with the maximum period permitted by the hospital, institution, or private practice.

During data entry, range and missing data checks will be performed on-line. The checks to be performed will be documented in the Data Monitoring Plan for the study. A summary report (QC Report) of these checks together with any queries resulting from manual review of the eCRFs

will be generated for each site and transmitted to the site and the site monitor. Corrections will be made by the study site personnel. This will be done on an ongoing basis.

### **13.3 Confidentiality**

There is a slight risk of loss of confidentiality of subject information. All records identifying the subject will be kept confidential and, to the extent permitted by the applicable laws and/or regulations, will not be made publicly available.

Information collected will be maintained on secure, password protected electronic systems. Paper files that contain personal information will be kept in locked and secure locations only accessible to the study team. Samples that are collected will be identified by a subject study number assigned at the time of registration to the trial. Any material issued to collaborating researchers will be anonymized and only identified by the subject study number.

Subjects will be informed in writing that some organizations including the sponsor-investigator and his/her research associates, HCRN, Bayer, IRB, or government agencies, like the FDA, may inspect their medical records to verify the information collected, and that all personal information made available for inspection will be handled in strictest confidence and in accordance with local data protection laws.

If the results of the study are published, the subject's identity will remain confidential.

### **13.4 Changes to the Protocol**

Study procedures will not be changed without the mutual agreement of the sponsor-investigator, HCRN, and Bayer Pharmaceuticals.

If it is necessary for the study protocol to be amended, the amendment or a new version of the study protocol (amended protocol) will be generated by the HCRN and must be approved by each IRB, Bayer Pharmaceuticals, and if applicable, also the local regulatory authority. Local requirements must be followed.

If a protocol amendment requires a change to the Written Informed Consent Form, then the IRB must be notified. Approval of the revised Written Informed Consent Form by the IRB is required before the revised form is used.

The site investigator is responsible for the distribution of these documents to his or her IRB, and to the staff at his or her center. The distribution of these documents to the regulatory authority will be handled according to local practice.

Bayer Pharmaceuticals' willingness to supply study drug is predicated upon the review of the protocol. HCRN agrees to provide written notice to Bayer Pharmaceuticals of any modifications to the protocol or informed consent.

## 14 ETHICS

### 14.1 Ethics Review

The final study protocol, including the final version of the Written Informed Consent Form, must be approved in writing by an IRB. The site investigator must submit written approval to the HCRN office before he or she can enroll any subject into the study.

The site investigator is responsible for informing the IRB of any amendment to the protocol in accordance with local requirements. In addition, the IRB must approve all advertising used to recruit subject for the study. The protocol must be re-approved by the IRB annually, as local regulations require.

Progress reports and notifications of serious unexpected adverse drug reactions will be provided to the IRB according to local regulations and guidelines.

The site investigator is also responsible for providing the IRB with reports of any serious adverse drug reactions from any other study conducted with the investigational product. Bayer Pharmaceuticals will provide this information to the sponsor-investigator. These reports will be reviewed by the sponsor-investigator and those considered unexpected and possibly related to protocol therapy and all deaths within 30 days of discontinuing treatment will be forwarded to participating sites for submission to their Institutional Review Boards per their guidelines. All other events will be held and submitted to the sites for continuing review.

### 14.2 Ethical Conduct of the Study

The study will be performed in accordance with ethical principles originating from the Declaration of Helsinki, which are consistent with ICH/Good Clinical Practice, and applicable regulatory requirements.

### 14.3 Informed Consent Process

The site investigator will ensure the subject is given full and adequate oral and written information about the nature, purpose, possible risks and benefits of the study. Subject must also be notified they are free to discontinue from the study at any time. The subject should be given the opportunity to ask questions and allowed time to consider the information provided. The subject's signed and dated informed consent must be obtained before conducting any procedure specifically for the study. The site investigator must store the original, signed Written Informed Consent Form. A copy of the signed Written Informed Consent Form must be given to the subject.

### List of medications to be used with caution during study drug treatment

Category	Drug Name
Moderate CYP3A4/5 inhibitors	Amprenavir, atazanavir, casopitant, cimetidine, darunavir, diltiazem, fosamprenavir, lomitapide, netupitant, tofisopam, verapamil
Moderate CYP3A4/5 inducers	Bosentan, efavirenz, etravirine, genistein, lersivirine, modafinil, nafcillin, talviraline
Sensitive CYP3A4/5 substrates 	Alpha-dihydroergocryptine, almorexant, alpaviroc, apixaban (doses <2.5 mg only), atazanavir, atorvastatin, avanafil, bosutinib, brecanavir, brotizolam, budesonide, buspirone, capravirine, casopitant, darifenacin, darunavir, ebastine, eletriptan, eplerenone, felodipine, fluticasone, ivacaftor, lomitapide, lumefantrine, lurasidone, maraviroc, midazolam, perospirone, quetiapine, ridaforolimus, sildenafil, ticagrelor, tilidine, tolvaptan, triazolam, vardenafil, vicriviroc, voclosporin
Strong BSEP inhibitors	Bosentan, fusidate, glibenclamide, sulindac, troglitazone (TGZ-sulfate)
Medications that carry a possible risk for QT prolongation 	Alfuzosin, apomorphine, aripiprazole, atazanavir, atomoxetine, bedaquiline, clozapine, dexmedetomidine, dolasetron, eribulin, famotidine, felbamate, fingolimod, foscarnet, gatifloxacin, gemifloxacin, granisetron, iloperidone, isradipine, lithium, mirabegron, mirtazapine, moexipril, norfloxacin, ofloxacin, olanzapine, ondansetron (4 mg or 8 mg), oxytocin, paliperidone, pasireotide, pipamperone, promethazine, quetiapine, ranolazine, rilpivirine, risperidone, roxithromycin, sertindole, telavancin, tetrabenazine, tizanidine, tolterodine, vardenafil, ziprasidone
MATE1 and OCT2 substrates 	Acyclovir, amantadine, amiloride, cephalexin, cephadrine, cimetidine, famotidine, fexofenadine, memantine, metformin (also a substrate for OCT1,

	MATE1, and MATE2K), pindolol, procainamide, ranitidine, and varencicline
BCRP substrates	Rosuvastatin, sulfasalazine
1	Sensitive substrates: Drugs whose plasma AUC values have been shown to increase 5-fold or higher when co-administered with a potent inhibitor.
2	Source: www.qtdrugs.org (as of Apr 7, 2015)
3	Source: FDA Draft Guidance for Industry, Drug Interaction Studies – Study Design, Data Analysis, and implications for Dosing and Labeling (February 2012) and Yonezawa and Inui (2011) Importance of the multidrug and toxin extrusion MATE/SLC47A family to pharmacokinetics, pharmacodynamics/toxicodynamics and pharmacogenomics. Br J Pharmacology 164:1817-25

## Appendix 2

